# **SCHEMA**

#### 1. BACKGROUND AND RATIONALE

# 1.1 Disease Background

The prognosis of pancreas adenocarcinoma (PCA) remains poor with little progress made in the last few decades with the exception of FOLFIRINOX (PRODIGE 4/ACCORD 11)  and gemcitabine/nab-Paclitaxel (MPACT trial)  treatments in 2011 and 2013, respectively, changing the PCA management paradigm with a median overall survival (OS), at best, reaching 11.1 months. Despite these advances, there is a continuous need to improve survival through the investigation of molecularly targeted agents.

Vascular endothelial growth factor (VEGF) and VEGF receptor (VEGFR)-mediated signaling and angiogenesis contribute to the pathogenesis and progression of PCA.  VEGF is expressed in all PCA tumors.  VEGF-A/VEGFR-2 signaling plays an important role in inducing invasion and migration of PCA cells.  VEGFR-2 and phosphorylated-VEGFR-2 (pVEGFR-2) are expressed in 69% and 50% of 107 PCA. The pVEGFR-2 is significantly associated with invasion of the anterior capsule of pancreas and arteries. It is proposed that the expression of these receptors is an important predictive and prognostic factor in PCA treatment. 

Results from anti-angiogenic agents studied in advanced PCA failed to significantly improve primary outcomes. The use of bevacizumab was evaluated in the AViTA Trial (Addition of bevacizumab to gemcitabine and erlotinib) and the reported negative primary outcome (OS). Another phase III trial with gemcitabine and bevacizumab (10 mg/kg) combination compared to gemcitabine alone (CALGB 80303) proved same outcomes (*P*= 0.95). Axitinib, in a phase III trial, compared gemcitabine/Axitinib to gemcitabine alone in the same setting, and yielded no significant difference in overall survival (OS). Interestingly, and challenging the findings from single agent backbone studies, the combination of gemcitabine and a fluoropyrimidine (5FU or capecitabine) with bevacizumab reached their primary endpoints in two separate single arm phase II trials. Additionally, a pooled analysis of 300 subjects enrolled in all single arm phase II trials utilizing gemcitabine-based doublets with bevacizumab proved survival advantage compared to historical controls. These studies demonstrate the feasibility of building upon more intensive chemotherapy backbones, specifically those including a fluoropyrimidine with bevacizumab combinations in PCA.

As suggested above, the choice of a chemotherapeutic backbone may impact the efficacy of anti-angiogenic therapy in PCA. In a preclinical study, the anti-tumor activity of fluoropyrimidines but not that of gemcitabine caused the release of bone marrow derived circulating endothelial progenitor cells (CEPs) and Tie-2 expressing monocytes (TEMs) as well as the induction of pro-angiogenic growth factors. Anti-angiogenic agents inhibit the CEP and TEM mobilization and pro-angiogenic signaling and thus enhance significantly the anti-tumor activity of fluoropyrimidines but not that of gemcitabine.  Additionally, gemcitabine-induced myelosuppression in subjects with PCA was found to interfere with the mobilization of pro-angiogenic cell types targeted by bevacizumab and may further counteract anti-angiogenic therapy by substantially reducing the angiogenesis inhibitor TSP-1.  These findings may explain why gemcitabine does not elicit TEM and CEP recruitment and may therefore lack synergy with anti-VEGF agents. This phenomenon is not known to

Version Date: 13AUG2018 Confidential Page 10 of 51

occur with fluoropyrimidines. FOLFIRINOX, a combination of a fluoropyrimidine, oxaliplatin and irinotecan, proved to have a large and significant survival advantage over gemcitabine alone in advanced PCA,  thus the choice of FOLFIRINOX combination in our proposed trial. The AViTA Trial (Addition of bevacizumab to gemcitabine and erlotinib) suggests that a subset of PCA subjects with elevated VEGF-A or VEGFR-2 levels may benefit from bevacizumab. 

# 1.2 Ramucirumab Clinical Experience

Ramucirumab (RAM) (IMC-1121B, trade name Cyramza) is a fully human monoclonal antibody (IgG1) directed mainly against VEGFR-2. RAM also blocks binding of VEGFR ligands, VEGF-A, VEGF-C, and VEGF-D. As a result, RAM inhibits ligand-stimulated activation of VEGFR-2, thereby inhibiting ligand-induced proliferation, and migration of human endothelial cells. RAM received its first global approval by the FDA on April 21, 2014 as monotherapy in the treatment of advanced or metastatic gastric cancer or gastroesophageal junction (GEJ) adenocarcinoma subjects who experience disease progression on or after 5FU- or platinum-containing chemotherapy. This approval was granted following the results of the REGARD trial, which compared RAM, as a single agent, to placebo in second line treatment of gastric and GEJ adenocarcinomas.  RAM had significant OS benefit when combined to paclitaxel in advanced/metastatic gastric and GEJ adenocarcinoma in the second line setting (RAINBOW trial).  These results have shifted the treatment paradigm in the treatment of gastric and GEJ cancers despite the initial disappointments with phase II trials utilizing another anti-angiogenic agent, bevacizumab. 19- These negative results were reflected in the international, randomized phase III AVAGAST (Avastin for Advanced Gastric Cancer) study, in which 774 subjects with advanced gastric or GEJ adenocarcinoma were randomized to a cisplatin/capecitabine with bevacizumab or placebo.  Given these opposing results between bevacizumab and RAM in gastric and GEJ cancers, it is becoming clearer that blocking VEGFR-2 (RAM) has a likely advantage over blocking VEGF-A (bevacizumab). More recently, the RAISE trial demonstrated the benefit of using ramucirumab in the setting of metastatic colorectal cancer. This trial compared ramucirumab versus placebo in combination with FOLFIRI in the second line setting for subjects with metastatic colorectal carcinoma. In this study, 536 subjects were assigned to each arm and ramucirumab plus FOLFIRI significantly improved OS with a manageable side effect profile.

Currently there are no validated predictive biomarkers for selecting which cancer subjects will benefit from anti-angiogenic therapy. Albumin has shown to play a role as a prognostic factor in advanced stage bevacizumab treated PCA subjects. A pooled analysis of 7 prospective trials showed that normal albumin levels (>3.4 g/dL) were associated with significantly improved median OS (10.2 months vs. 4.1 months; P=0.0001), median time to tumor progression (TTP) of 6.2 vs. 3.7 months (P=0.0488), and disease control rate (71% vs. 46%; P=0.007) for subjects receiving bevacizumab, but not for those treated without bevacizumab. 

Version Date: 13AUG2018 Confidential Page 11 of 51

#### 2. STUDY OBJECTIVES AND ENDPOINTS

# 2.1 Objectives

# 2.1.1 Primary Objective

Estimate and compare PFS of mFOLFIRINOX plus ramucirumab (RAM) versus mFOLFIRINOX plus placebo in subjects with recurrent or metastatic pancreas cancer (PCA) who present for first line chemotherapy treatment.

# 2.1.2 Secondary Objectives

- Estimate and compare the median overall survival (mOS) in each arm.
- Evaluate and compare the response rate (RR) in each arm.
- Evaluate and compare the toxicities in each arm.

# 2.2 Endpoints

# 2.2.1 Primary Endpoint

Nine month PFS is based upon the time of registration until progression or death. Disease is evaluated by CT/MRI scans of the organ(s) with the target lesion(s) based on RECIST 1.1 criteria.

# 2.2.2 Secondary Endpoints

- Median overall survival (mOS) will be measured using the Kaplan-Meier method.
- Response rate (RR) will be evaluated per RECIST 1.1
- Toxicity evaluation will be assessed per CTCAE v4

#### 3. ELIGIBILITY CRITERIA

Each of the criteria in the checklist that follows must be met in order for a subject to be considered eligible for this study.

# 3.1 Inclusion Criteria

- 1. Written informed consent and HIPAA authorization for release of personal health information. **NOTE:** HIPAA authorization may be included in the informed consent or obtained separately.
- 2. Age  $\geq$  18 years at the time of consent.
- 3. ECOG Performance Status of 0-1 within 7 days prior to registration.
- 4. Histologic or cytological diagnosis of recurrent or metastatic pancreas adenocarcinoma (PCA) who present for first line chemotherapy treatment.
- 5. No prior first line systemic treatment (prior adjuvant or neoadjuvant treatment is permitted). Subjects whose disease has progressed after 6 months of last systemic chemotherapy or chemo-radiation in the adjuvant or neoadjuvant setting are eligible.
- 6. Measurable disease determined using guidelines of RECIST 1.1. Baseline tumor assessment should be performed using high resolution CT scans or MRI.
- 7. Urine protein < 1+ on dipstick test or routine urinalysis. If the proteinuria on these tests is  $\ge 2+$ , then a 24-hour urine test must be collected and must demonstrate < 1 g protein in 24 hours to allow participation

Version Date: 13AUG2018 Confidential Page 12 of 51

- 8. Estimated life expectancy of > 12 weeks, as assessed by the site investigator.
- 9. If sexually active, must be postmenopausal, surgically sterile, or using effective contraception (hormonal or barrier methods) due to unknown risk of teratogenicity of ramucirumab
- 10. Demonstrate adequate organ function as defined in Table 1 below; all screening labs to be obtained within 7 days prior to registration. Include additional labs or remove as needed below and ensure they are included in the Study Calendar and Evaluations Section

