**Table 1: Organ Function Requirements** 

System	Laboratory Value
Hematological	•
Hemoglobin	$\geq$ 9 g/dL
Absolute Neutrophil Count (ANC)	$\geq 1,500/\text{mm}^3$
Platelet Count (PLT)	$\geq 100,000/\text{mm}^3$
Renal	
Creatinine or	$\leq 1.5 \text{ mg/dL}$
Creatinine clearance 	≥ 40 mL/min
Albumin	$\geq$ 2.5 g/dL
Hepatic	
Bilirubin	$\leq 1.5 \text{ mg/dL}$
Aspartate aminotransferase (AST)	$\leq$ 3 × ULN
	or $< 5 \times ULN$ in the setting
	of liver metastases
Alanine aminotransferase (ALT)	$\leq$ 3 × ULN
	or $< 5 \times ULN$ in the setting
	of liver metastases
Coagulation	
International Normalized Ratio (INR)	The subject has adequate
	coagulation function as
Patients receiving warfarin must be	defined by International
switched to low molecular weight	Normalized Ratio (INR)
heparin and have achieved stable	≤1.5 and a partial
coagulation profile prior to first dose	thromboplastin time (PTT)
of protocol therapy	(PTT/aPTT) < 1.5 x
	ULN.).

<sup>1: If serum creatinine is >1.5 times the ULN, a 24-hour urine collection to calculate creatinine clearance must be performed.

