# 7.1 Screening

# 7.1.1 Within 28 Days Prior to Registration for Protocol Therapy:

The following should be collected before registration for protocol therapy:

- Prior to the subject being registered to the study, confirmation of diagnosis must be obtained via pathology report including staging information.
- Medical history and Height
- Physical examination
- Vitals Signs (including blood pressure), Weight [kg] and ECOG PS
- Laboratory Testing:
  - CBC with differential: Hemoglobin, hematocrit, erythrocyte count (RBC), mean cell volume, mean cell hemoglobin concentration, leukocytes (WBC), neutrophils, lymphocytes, monocytes, basophils, platelets.
  - CMP: Sodium, potassium, total bilirubin, alkaline phosphatase, alanine aminotransferase (ALT), aspartate aminotransferase (AST), blood urea nitrogen (BUN), creatinine, calcium, random glucose, albumin
  - o Magnesium and uric acid
  - o Coagulation tests: PT, INR and PTT; coagulation tests should be periodically repeated during the course of the study per site investigator discretion.
  - o CA 19-9
  - Thyroid function (TSH, total T3, free T4). If the TSH is abnormal, a total T3 and free T4 should be ordered.
  - Serum pregnancy test for women of child-bearing potential must be performed within 7 days prior to first dose of study treatment
  - o Urinalysis including a urine dipstick for protein if quantification needed
- Radiological assessment (CT or MRI of chest, abdomen, and pelvis) with tumor measurements. Pre-treatment scans to be performed within 28 days prior to registration.

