## 11.9 Analysis Datasets

The intention-to-treat (ITT) analysis dataset includes all subjects who meet the eligibility criteria and are registered onto the study irrespective of their compliance to the planned course of treatment. The intention-to-treat principle asserts that the effect of a treatment policy can be best assessed by evaluating on the basis of the intention to treat a subject (i.e. the planned treatment regimen) rather than the actual treatment given. It has the consequence that subjects allocated to a treatment group should be followed up, assessed and analyzed as members of that group irrespective of their compliance to the planned course of treatment

The safety analysis dataset includes all subjects who are randomized and receive at least one dose of study treatment (on either arm). Subjects will be analyzed for safety according to the treatment actually received.

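### Inclusion criterion 7 gives a 1+ urine protein result no route into the trial while a worse result has one; separately, the Section 11.9 ITT set lets any subject ruled ineligible after randomization be dropped from the primary PFS analysis

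*Combined protocol and SAP*

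**What the plan says.** **Entry rule.** Criterion 7 has two sentences, worded the same in the synopsis and in Section 3.1. The first requires "Urine protein < 1+ on dipstick test or routine urinalysis". The second begins "If the proteinuria on these tests is" 2+ or higher, and continues "then a 24-hour urine test must be collected and must demonstrate < 1 g protein in 24 hours to allow participation". Section 3 makes every item mandatory: "Each of the criteria in the checklist that follows must be met in order for a subject to be considered eligible for this study". The screening list in Section 7.1.1 adds only "Urinalysis including a urine dipstick for protein if quantification needed" and describes no other path for a 1+ result.

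**Analysis set.** Section 11.9 says the ITT set "includes all subjects who meet the eligibility criteria and are registered onto the study irrespective of their compliance to the planned course of treatment". The same section goes on to state the intention-to-treat principle: people allocated to an arm are to be followed, assessed and analysed in that arm. Section 11.4 uses this set for the one-sided log-rank test on PFS, and Section 11.5 uses it for OS and response rate. The safety set in Section 11.9 needs only randomization and one dose, with no eligibility condition.

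**The concern.** There are two faults. They are linked only in that an ambiguous entry criterion is a likely place for a later dispute about eligibility.

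First, the two sentences of criterion 7 do not meet. One cut-off lies below 1+ and the other starts at 2+, so the level between them fails the first sentence and never reaches the second. One site may screen out a 1+ patient; another may admit the patient because only 2+ calls for a further test. Proteinuria is a listed adverse event of ramucirumab (Section 9.1.5) with its own dose rules (Section 6.1.2), so uneven entry at 1+ is relevant to safety.

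Second, an ITT set that depends on meeting eligibility allows exclusions after randomization. Section 12.2 says a monitor may verify eligibility, so a ruling can come after a subject has been randomized. Section 11.9 does not say who makes the ruling, or that it must be made blind to arm and outcome. A dosed subject ruled ineligible would count for toxicity but not for PFS.

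**Working it through.** **1. Each urine result against criterion 7, read literally**

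| Result | First sentence (below 1+) | Second sentence (2+ or higher) | Disposition |
|---|---|---|---|
| Negative or trace | met | not triggered | eligible |
| 1+ | not met | not triggered | fails, no further test |
| 2+ or higher, under 1 g/24 h | not met | triggered and passed | may participate |
| 2+ or higher, 1 g/24 h or more | not met | triggered and failed | not eligible |

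The 1+ level is the only one with neither acceptance nor a confirmatory test.

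**2. When the analysis set is affected**

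- A 1+ patient is screened out: never randomized, in no analysis set.
- A 1+ patient is admitted and everyone treats this as eligible: stays in the ITT set.
- A 1+ patient is admitted, randomized and later ruled ineligible: can be dropped from PFS, OS and response.

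Only the third path changes the analysis. It is open in the same way for every other inclusion and exclusion criterion.

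**3. Reproducing the plan's sample size, as a base for the power loss**

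Inputs from Section 11.10: median PFS 6 and 9 months (hazard ratio 6/9 = 0.6667), one-sided alpha 0.20, power 0.80, accrual A = 24 months, follow-up F = 9 months, 43 + 42 = 85 subjects. Assumed: exponential PFS and uniform accrual.

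Event probability = 1 − [exp(−λF) − exp(−λ(A+F))]/(λA), with λ = ln 2/median:

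- control (λ = ln 2/6): 0.880
- ramucirumab (λ = ln 2/9): 0.772
- average weighted 43:42: 0.827

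Events needed, with z = 0.8416 for both alpha and power:

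- Schoenfeld: 4(0.8416 + 0.8416)²/(ln 0.6667)² = 68.9, so 69; 69/0.827 = 83.4, so N = 84
- Freedman: (0.8416 + 0.8416)² × [(1 + 0.6667)/(1 − 0.6667)]² = 70.8, so 71; 71/0.827 = 85.9, so N = 86

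The planned 85 lies between the two. At N = 85 about 85 × 0.827 = 70.3 events are expected. Power is 0.805 (Schoenfeld) or 0.798 (Freedman), against the stated 0.8014. The plan's figure is reproduced, and this point does not dispute it.

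**4. Power if k of 85 are removed**

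The documents give no rate, so k runs from 0 to 9; 9 is 10% of 85 (8.5) rounded up. With d = (85 − k) × 0.827 events, Schoenfeld power is Φ(√d × 0.4055/2 − 0.8416) and Freedman power is Φ(√d × 0.2 − 0.8416).

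| k removed | N left | Events | Schoenfeld | Freedman |
|---|---|---|---|---|
| 0 | 85 | 70.3 | 0.805 | 0.798 |
| 2 | 83 | 68.6 | 0.799 | 0.793 |
| 4 | 81 | 67.0 | 0.793 | 0.787 |
| 6 | 79 | 65.3 | 0.787 | 0.781 |
| 9 | 76 | 62.8 | 0.778 | 0.772 |

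Even the largest assumed removal costs less than three percentage points of power.

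**The case against.** The strongest reply is that the two faults should not be run together. A reader might infer that criterion 7 itself decides who is in the primary analysis. The documents do not support that. Removal needs a subject admitted by the site and later ruled ineligible by someone reading the rule more strictly, and no section describes such a ruling for urine protein. The eligibility condition in Section 11.9 is general, and proteinuria does not make it worse. This stands, and the two parts are therefore kept separate here.

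A reader might also put a count on it, for example 2% to 10% of 85 subjects. That rate would be invented. It would also require every 1+ patient to be admitted and then removed, although the literal rule bars them. The lower bound is zero.

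A third tempting reading is that Table 1 has the same dead end for creatinine, because the limit is 1.5 mg/dL while the footnote opens "If serum creatinine is >1.5 times the ULN". It does not. Table 1 accepts creatinine clearance of at least 40 mL/min as an alternative, and the footnote says when a 24-hour collection is mandatory, not that clearance may be obtained only then. Any gap also depends on a ULN that the documents do not give. At 1.0 mg/dL the two limits coincide; at an assumed 1.2 the trigger would be 1.5 × 1.2 = 1.8 mg/dL; below 1.0 the order reverses. At most the units need tidying.

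Three mitigating points also stand. Urine protein is checked before each cycle (study calendar, note 6), and Section 6.1.2 has rules for proteinuria on treatment. A dosed subject stays in the safety set whatever the ruling. The dipstick is read before randomization in a double-blind trial, so bias between arms is probably limited.

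Finally, the principle in Section 11.9 is worded mainly around compliance, so it could be said not to address eligibility. But it is expressed in terms of subjects allocated, and an eligibility filter removes allocated subjects.

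**Conclusion.** Both faults are on the face of the text. Criterion 7 is internally inconsistent in both places where it appears: 1+ has no way in and a higher result does, so handling may vary between sites. Section 11.9 gives the name ITT to a set from which randomized subjects can be removed after an eligibility ruling, which departs from the principle stated in that section and reaches PFS, OS and response rate.

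The practical size is small. The number affected is unknown and may be zero. If as many as 9 of 85 were removed, power would fall from 0.805 to 0.778 (Schoenfeld) or from 0.798 to 0.772 (Freedman), assuming exponential PFS, uniform accrual and the same event rate in those removed. The view that bias between arms is limited rests on eligibility being judged on pre-randomization data and without knowledge of arm; Section 11.9 does not secure the latter. This is a minor point, worth correcting because the correction is only wording.

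**What to change.** - **Criterion 7, synopsis and Section 3.1:** reconcile the two sentences so that negative or trace, 1+, and 2+ or higher each have exactly one disposition. The cut-offs are a clinical decision for the sponsor.
- **Section 11.9:** define the ITT set as all randomized subjects, analysed in the arm to which they were allocated. Use it for PFS, OS and response rate as Sections 11.4 and 11.5 already intend.
- **Sensitivity analysis:** add an eligible-only analysis of PFS, with eligibility judged from pre-randomization data by people blind to arm and outcome.
- **Table 1 and its footnote, synopsis and Section 3.1:** optionally express creatinine in one unit, as a tidy-up.

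The cost is an amendment to eligibility and analysis-set wording. It needs no additional subjects, visits or tests beyond whatever disposition the sponsor chooses for a 1+ result.

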**Table 1: Organ Function Requirements** 

System	Laboratory Value
Hematological	•
Hemoglobin	$\geq$ 9 g/dL
Absolute Neutrophil Count (ANC)	$\geq 1,500/\text{mm}^3$
Platelet Count (PLT)	$\geq 100,000/\text{mm}^3$
Renal	
Creatinine or	$\leq 1.5 \text{ mg/dL}$
Creatinine clearance 	≥ 40 mL/min
Albumin	$\geq$ 2.5 g/dL
Hepatic	
Bilirubin	$\leq 1.5 \text{ mg/dL}$
Aspartate aminotransferase (AST)	$\leq$ 3 × ULN
	or $< 5 \times ULN$ in the setting
	of liver metastases
Alanine aminotransferase (ALT)	$\leq$ 3 × ULN
	or $< 5 \times ULN$ in the setting
	of liver metastases
Coagulation	
International Normalized Ratio (INR)	The subject has adequate
	coagulation function as
Patients receiving warfarin must be	defined by International
switched to low molecular weight	Normalized Ratio (INR)
heparin and have achieved stable	≤1.5 and a partial
coagulation profile prior to first dose	thromboplastin time (PTT)
of protocol therapy	(PTT/aPTT) < 1.5 x
	ULN.).

<sup>1: If serum creatinine is >1.5 times the ULN, a 24-hour urine collection to calculate creatinine clearance must be performed.

# 3.2 Exclusion Criteria

- 1. Subjects with histology other than adenocarcinoma; Examples include: neuroendocrine tumors, acinar cell cancer, sarcoma or lymphoma of the pancreas
- 2. Ongoing or active infection
- 3. Symptomatic congestive heart failure, unstable angina pectoris, symptomatic or poorly controlled cardiac arrhythmia. Symptomatic heart failure (NYHA Class II-IV)

Version Date: 13AUG2018 Confidential Page 13 of 51

- 4. Uncontrolled or poorly-controlled hypertension (>160 mmHg systolic or > 100 mmHg diastolic for >4 weeks) despite standard medical management.
- 5. Acute or sub-acute intestinal obstruction
- 6. Interstitial pneumonia or interstitial fibrosis of the lung, which in the opinion of the site investigator could compromise the subject or the study
- 7. Pleural effusion or ascites that causes > grade 1 dyspnea
- 8. Cirrhosis at a level of Child-Pugh B (or worse) or cirrhosis (any degree) with a history of hepatic encephalopathy or clinical meaningful ascites resulting from cirrhosis; clinically meaningful ascites is defined as ascites resulting from cirrhosis and requiring ongoing treatment with diuretics and/or paracentesis
- 9. Grade 3 or higher bleeding event  $\leq$  3 months prior to randomization.
- 10. Experience of any arterial thrombotic or arterial thromboembolic events, including, but not limited to myocardial infarction, transient ischemic attack, or cerebrovascular accident,  $\leq 6$  months prior to randomization.
- 11. History of deep vein thrombosis, pulmonary embolism, or any other significant thromboembolism (venous port or catheter thrombosis or superficial venous thrombosis are not considered "significant") during the 3 months prior to randomization.
- 12. GI perforation/fistula
- 13. Documented and/or symptomatic or known brain or leptomeningeal metastases.
- 14. Severely immune-compromised (other than being on steroids) including known HIV infection
- 15. Concurrent active malignancy, other than adequately treated non-melanoma skin cancer, other noninvasive carcinoma, or in situ neoplasm. A subject with previous history of malignancy is eligible, provided that he/she has been disease-free for > 3 years.
- 16. Breast-feeding or pregnant. Serum pregnancy test for women of child-bearing potential must be performed within 7 days prior to first dose of study treatment
- 17. Prior autologous or allogeneic organ or tissue transplantation.
- 18. Known allergy to any of the treatment components
- 19. The patient has undergone major surgery within 28 days prior to first dose of protocol therapy, or minor surgery/subcutaneous venous access device placement within 2 days prior to first dose of protocol therapy. The patient has elective or planned major surgery to be performed during the course of the clinical trial.
- 20. Have any condition that does not permit compliance with the study schedule including psychological, geographical, or medical.
- 21. Receiving medications that can effect clotting ability: warfarin, aspirin (once-daily aspirin use- maximum dose 325 mg/day is permitted), nonsteroidal anti-inflammatory drugs (NSAIDs, including ibuprofen, naproxen, and others), dipyridamole or clopidogrel, or similar agents.
- 22. The patient has a serious or non-healing wound, ulcer, or bone fracture within 28 days prior to first dose of protocol therapy.

Version Date: 13AUG2018 Confidential Page 14 of 51

